7.7 Withdrawal criteria

Any participant is free to withdraw from the study at any time for any reason without prejudice to future care, and with no obligation to give the reason for withdrawal. We will no longer contact the participant, but may with the participant's permission retain and use information provided previously, obtain and use information from the participant's health records or interview them about their study experience.

7.8 Assessment and management of risk

This study does not impact on routine NHS care and follows existing NICE guidance for all aspects of care provided to patients. This study will not use any investigational medicinal products. We therefore do not expect patients to come to harm.

7.9 End of study (Stage 2)

The end of the study is defined as when the last participant has attended their sixth month (final) followup assessment.

8. SAMPLES

No clinical samples will be obtained as part of this research outside usual NHS care.

9. Recording and reporting of SAEs

9.1 Definitions

Term	Definition
Adverse Event (AE)	Any untoward medical occurrence in a patient or clinical investigation participants, which does not necessarily have to have a causal relationship with this treatment.
	An AE can therefore be any unfavourable and unintended sign (including an abnormal laboratory finding), symptom or disease temporally associated with the the study, whether or not considered related to the study.

Adverse Reaction (AR)	An untoward and unintended response in a participant to an investigational medicinal product which is related to any dose administered to that participant. The phrase "response to an investigational medicinal product" means that a causal relationship between a trial medication and an AE is at least a reasonable possibility, i.e. the relationship cannot be ruled out. All cases judged by either the reporting medically qualified professional or the Sponsor as having a reasonable suspected causal relationship to the trial medication qualify as adverse reactions. It is important to
	SmPC. It is specifically a temporal relationship between taking the drug, the half-life, and the time of the event or any valid alternative etiology that would explain the event.
Serious Adverse Event (SAE)	 A serious adverse event is any untoward medical occurrence that: results in death is life-threatening requires inpatient hospitalisation or prolongation of existing hospitalisation results in persistent or significant disability/incapacity consists of a congenital anomaly or birth defect Other 'important medical events' may also be considered serious if they jeopardise the participant or require an intervention to prevent one of the above consequences. NOTE: The term "life-threatening" in the definition of "serious" refers to an event in which the participant was at risk of death at the time of the event; it does not refer to an event which hypothetically might have caused death if it were more severe.
Serious Adverse Reaction (SAR)	An adverse event that is both serious and, in the opinion of the reporting Investigator, believed with reasonable probability to be due to one of the trial treatments, based on the information provided.
Expected Serious Adverse Events/Reactions	This study does not impact on routine NHS care and follows existing NICE guidance for all aspects of care provided to patients. This study will not use any investigational medicinal products. We therefore do not expect patients to come to harm.
Suspected Unexpected Serious Adverse Reaction (SUSAR)	 A serious adverse reaction, the nature and severity of which is not consistent with the information about the medicinal product in question set out in the reference safety information: in the case of a product with a marketing authorisation, this could be in the summary of product characteristics (SmPC) for that product, so long as it is being used within it's licence. If it is being used off label an assessment of the SmPCs suitability will need to be undertaken. in the case of any other investigational medicinal product, in the investigator's brochure (IB) relating to the trial in question

9.2 Reporting procedures for All Adverse Events

All AEs occurring during the study observed by the investigator or reported by the participant, whether or not attributed to study, will be recorded on the CRF.

The following information will be recorded: description, date of onset and end date, severity, assessment of relatedness to study, other suspect device and action taken. Follow-up information should be provided as necessary.

AEs considered related to the study as judged by a medically qualified investigator or the sponsor will be followed until resolution or the event is considered stable. All related AEs that result in a participant's withdrawal from the study or are present at the end of the study, should be followed up until a satisfactory resolution occurs.

It will be left to the investigator's clinical judgment whether or not an AE is of sufficient severity to require the participant's removal from treatment. A participant may also voluntarily withdraw from treatment due to what he or she perceives as an intolerable AE. If either of these occurs, the participant must undergo an end of study assessment and be given appropriate care under medical supervision until symptoms cease or the condition becomes stable.

The severity of events will be assessed on the following scale: 1 = mild, 2 = moderate, 3 = severe.

The relationship of AEs to the study will be assessed by a medically qualified investigator.

9.3 Reporting Procedures for Serious Adverse Events

All SAEs occurring from the time of written informed consent until the end of the study must be reported to the Sponsor immediately and within 24 hours of becoming aware of the event. The SAE will be reported using appropriate forms and according to the Sponsor SOP for reporting serious adverse events. Additional information will be provided if requested to the Sponsor and main Research Ethics Committee (REC). The Principal Investigator or another delegated physician (as agreed by the Sponsor) is responsible for the review and sign off of the SAE and the assessment of causality (i.e. whether an event is related to a study procedure or intervention).

The Sponsor will perform an initial check of the information and ensure that the SAE line listing is reviewed by the Director of Research & Innovation. All SAE information must be recorded on an SAE form and sent to the Sponsor. Additional information received for a case (follow-up or corrections to the original case) needs to be detailed on a new SAE form and sent to the Sponsor.

Copies of all documentation and correspondence relating to SAEs will be stored in the TMF and / or ISF.

The Sponsor will report all SUSARs to the Research Ethics Committee concerned. Fatal or lifethreatening SUSARs must be reported within 7 days and all other SUSARs within 15 days. The CI will inform all investigators concerned of relevant information about SUSARs that could adversely affect the safety of participants.

In addition to the expedited reporting above, the CI shall submit once a year throughout the study or on request an Annual Report to the Ethics Committee which lists all SAEs / SUSARs that have occurred during the preceding 12 months.

9.4 Responsibilities

All individual SAEs, AEs, ARs and trends in events and reactions will be independently reviewed in addition to usual study safety monitoring procedures by the SSG, which will convene at least every 3 months.

9.5 Reporting urgent safety measures

If any urgent safety measures are taken the CI/Sponsor shall immediately and in any event no later than 3 days from the date the measures are taken, give written notice to the Sponsor and the relevant REC of the measures taken and the circumstances giving rise to those measures.

10 STATISTICS AND DATA ANALYSIS

10.1 Sample size calculation

A total of at least 10 patients will be taking part in the **Stage 1** development focus-groups alongside a minimum of 10 experts / stakeholders, to allow a sufficient sample for qualitative analysis and development of the intervention.

For Stage 2, assuming that 30% of invitees will be recruited and in order to estimate the recruitment rate with a precision of +/- 8%, 30 participants will have to be recruited. Assuming a dropout rate of 25% and having recruited 30 individuals, the precision of the estimated retention rate during six months would be +/- 14%. This will also provide an ample sample size to draw on for qualitative interviewing. The decision to proceed to a definitive multicentre trial will be made on the basis of acceptable rates and time for recruitment and retention, as well as participant satisfaction. Detailed progression criteria will be drawn up in collaboration with an independently chaired Study Steering Committee upon completion of recruitment and follow-up.

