7.1 Recruitment

Stage 1: At least ten (10) individuals with AAA in surveillance will take part in the service-development workshops (as outlined above). We aim to have at least 45 responses to the scaffolding questionnaire from each stakeholder group (patient groups and expert groups). Further, at least five (5) expert stakeholders involved in the care of patients with an AAA in screening and surveillance programmes will also be asked to take part in focus-groups and interviews, to refine and finalise the cardiovascular-risk reduction intervention.

Stage 2: At least thirty (30) individuals with an AAA in the AAA screening and surveillance programme will be recruited and they will be followed-up over a minimum of six months. This will allow us to assess the primary outcome of interest (feasibility and acceptability). Participants that consent will be interviewed to further explore the feasibility of the intervention.

Further, at least five (5) expert stakeholders will be recruited to take part in interviews to assess the acceptability and fidelity of the intervention delivery by healthcare-staff in the participating NHS AAA screening and surveillance programmes.

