10.2 Statistical analysis plan

Recruitment, retention, measures-completion rates and participant satisfaction scores will be reported using descriptive statistics with 95% confidence intervals. Qualitative data will be transcribed verbatim and analysed. Intervention fidelity scores will be presented as mean scores and ranges for each intervention component and also broken down by facilitator to examine variation between provider staff. During fidelity scoring, examples of good practice will be extracted to use in training intervention providers for the main trial.

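### At the 95% level fixed in section 10.2, 30 recruits give about ±9 points on recruitment and ±15.5 on retention, not the ±8% and ±14% stated in section 10.1

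*Protocol*

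**What the plan says.** Protocol section 10.1 (Sample size calculation) sets the Stage 2 number in two steps.

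- Recruitment: "assuming that 30% of invitees will be recruited", it states that "in order to estimate the recruitment rate with a precision of +/- 8%, 30 participants will have to be recruited".
- Retention: "Assuming a dropout rate of 25% and having recruited 30 individuals", it states that "the precision of the estimated retention rate during six months would be +/- 14" per cent.

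The section gives no confidence level, no interval method and no number of men to be invited. Section 7.1 (Recruitment) repeats the target as a minimum: "At least thirty (30) individuals with an AAA in the AAA screening and surveillance programme will be recruited".

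The only confidence level given for these rates is in section 10.2 (Statistical analysis plan). There, recruitment, retention, completion of measures and satisfaction "will be reported using descriptive statistics with 95% confidence intervals".

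**The concern.** Every input needed to check the two half-widths is printed in section 10.1, apart from the confidence level. A reader will naturally take that level from section 10.2, which follows directly and covers the same two rates. At 95%, neither figure comes out, and both err in the favourable direction by a similar proportion.

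The two precisions are the only quantitative argument for 30 participants. Section 10.1 also makes recruitment and retention part of the basis for deciding on a definitive multicentre trial, with detailed progression criteria to be drawn up later. Whoever sets those criteria from section 10.1 would expect somewhat tighter estimates than the reported 95% intervals will show.

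**Working it through.** **Inputs**

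- Recruitment proportion 0.30, recruits 30 (section 10.1). Implied invitees: 30 / 0.30 = 100. The protocol does not print this number.
- Dropout 25%, so retention 0.75, with denominator 30 (section 10.1).
- Confidence level 95%, z = 1.96 (section 10.2).

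**Attempt to reproduce the stated figures**

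Normal-approximation half-width: z × √(p(1 − p)/n).

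- Recruitment: 1.96 × √(0.30 × 0.70 / 100) = 0.0898, or ±9.0 points (21.0% to 39.0%). Stated: ±8.
- Retention: 1.96 × √(0.75 × 0.25 / 30) = 0.1549, or ±15.5 points (59.5% to 90.5%). Stated: ±14.

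The half-widths are 8.98/8 = 1.12 and 15.49/14 = 1.11 times those stated, so about 12% and 11% wider.

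**Does another 95% method recover them?**

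Half-widths in percentage points. Since 75% of 30 is 22.5, both neighbouring whole counts are shown.

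| 95% method | 30/100 | 22/30 | 23/30 |
|---|---|---|---|
| Normal (Wald) | 9.0 | 15.8 | 15.1 |
| Wilson | 8.8 | 15.1 | 14.6 |
| Agresti-Coull | 8.9 | 15.3 | 14.8 |
| Jeffreys | 8.9 | 15.3 | 14.7 |
| Clopper-Pearson (exact) | 9.4 | 16.8 | 16.2 |

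Recruitment runs from 8.8 to 9.4 and retention from 14.6 to 16.8. No entry rounds to 8 or to 14.

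**What would deliver the stated precision at 95%?**

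Inverting: n = z² p(1 − p)/d².

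- ±8 on recruitment: 1.96² × 0.21 / 0.08² = 126.05, so 127 invitees; 127 × 0.30 = 38.1, about 38 recruits.
- ±14 on retention: 1.96² × 0.1875 / 0.14² = 36.75, so 37 recruits.
- At 38 recruits the half-widths are ±8.0 and ±13.8, so both hold.

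**What other level would fit 30 recruits?**

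- 90% normal approximation: ±7.5 and ±13.0. Neither stated figure is exactly met.
- Level implied under the normal approximation: z = 0.08/√(0.21/100) = 1.746 and z = 0.14/√(0.1875/30) = 1.771, about 92% in both cases.
- 90% exact (Clopper-Pearson): 30/100 gives 22.5% to 38.4%, ±7.96; 23/30 gives 60.6% to 88.5%, ±13.95; 22/30 gives ±14.5. This roughly reproduces both stated figures.

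**The case against.** The strongest reply is that section 10.1 never claims 95%. Section 10.2 governs how results will be reported, not how the sample was derived, and a 90% exact interval lands close to both stated figures with the protocol's own 30 recruits. That stands as arithmetic. It rules out two stronger readings that a reader might infer:

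- That no conventional confidence level can yield these figures. This is true of the normal approximation at 90% and 95%, but not of the 90% exact interval.
- That the figures were calculated for about 38 men and left in place when the target became 30. At 95% they do fit 37 to 38 recruits, but the protocol mentions no such number. Because 90% exact intervals at 30 fit about as well, their origin cannot be settled from the document.

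The reply does not clear the text. Neither a 90% level nor an exact method appears anywhere in the protocol. If one was used, section 10.1 promises precision on an unstated basis that differs from the one section 10.2 will report.

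The reply on importance carries more weight. Stage 2 is a single-arm feasibility cohort (section 4.2). The progression criteria are not yet numeric, and the decision also rests on time to recruit and participant satisfaction. Section 10.1 gives a further reason for 30, the pool for qualitative interviews. The reported 95% intervals will show the real uncertainty whatever section 10.1 says. These points lower the severity without making the two figures right. Nor does the minimum wording in section 7.1 help, because section 10.1 ties both precisions to 30.

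**Conclusion.** The point holds relative to the 95% level in section 10.2. With 30 recruits, the half-width is about ±9.0 points for recruitment against ±8 stated, and about ±15.5 points for retention against ±14 stated. The excess is about 1 point and 1.5 points by the normal approximation. For retention it is as small as 0.6 of a point with Wilson at 23 of 30.

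This rests on the protocol's assumed 30% uptake and 25% dropout, on 100 invitees (implied, not stated), and on carrying the 95% level back from section 10.2. A separate statistical analysis plan was not available. It might name a level or method, but it could not make ±8 and ±14 correct at 95% with 30 recruits.

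A reader might go further and conclude that 30 is too few and the study must recruit 38. The documents do not support that: no numeric progression threshold is given that ±9 would miss and ±8 would meet. This is a should-fix correction of the stated precision, not a reason to change the design.

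**What to change.** Keep 30 participants and replace the two precision statements in section 10.1 with text such as:

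> With about 100 men invited and 30 recruited (30%), the 95% CI half-width is about ±9 percentage points for the recruitment rate; with 25% dropout among 30 it is about ±15 to 16 points for six-month retention.

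Name the interval method in the same paragraph and use it for the intervals in section 10.2. The number of invitations should be printed because invitees, not recruits, are the denominator of the recruitment rate. The suggested retention range suits the normal approximation; if the exact method is chosen, the figures should be those for that method (about ±9.4 and ±16 to 17).

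If the present figures came from another confidence level or method, state it in section 10.1 and reconcile it with section 10.2. If ±8 and ±14 at 95% are truly required, the target would be about 127 invited and 38 recruited, but nothing in the protocol shows that they are.

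The cost is one paragraph of protocol text and a slightly less favourable stated precision. No extra patients are needed, and conduct and analysis do not change.

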3.2 Outcomes

The main outcome **Stage 1** of this study is a purpose-built cardiovascular risk reduction intervention for patients with AAA.

The main outcome measure of **Stage 2** is to assess the feasibility of using the purpose-built cardiovascular risk reduction intervention developed in Stage 1 in patients who have an AAA and who are being seen regularly in existing NHS AAA screening and surveillance centres.

Secondary outcome measures of interest for Stage 2 will include:

Proportion of patients agreeing to take part out of all patients invited (intervention recruitment rate); proportion of patients recruited who provide data at the end of the study period (intervention retention rate); all cardiovascular events; mortality; quality of life using the EuroQol-5D (EQ-5D) questionnaire; weight and other relevant anthropometric information including Body Mass Index (BMI); blood-pressure levels; self-reported medication adherence; smoking status (self-reported); uptake of smoking-cessation services; reason for dropout; low-density and high-density lipoprotein levels as well as routine biochemistry.

4 STUDY DESIGN and METHODS

4.1 STAGE 1 (Development of the cardiovascular-risk reduction intervention with patients and experts/stakeholders)

Completed preliminary work

Identification of the intervention objectives with Patient and Public Involvement (PPI) and expert input

Based on NICE guidance(1), Medical Research Council (MRC) complex-intervention guidance, a systematic literature review, and consultation with patients, GPs as well as cardiovascular experts, we have established the five key intervention targets:

- i. Smoking cessation: A clear and easy to follow pathway should be in place, including patientcentred discussion of barriers and referral to existing expert-services.
- ii. Lifestyle modifications: physical activity and diet should be assessed and individuals should (if needed) be supported in setting and achieving specific targets for change.
- iii. Antiplatelet agents: Aspirin 75mg (or Clopidogrel 75mg if Aspirin is contra-indicated) should be offered to all individuals.
- iv. Lipid control: High-intensity statin-therapy should be offered to all individuals regardless of baseline lipid levels

The antiplatelet and statin strategy are supported by NICE (document CG147) and European Society of Cardiology guidance(2, 3).

v. BP-control: A target of 140/90mmHg should be achieved using the NICE CG127 treatmentalgorithm.

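### The domains for the go/no-go decision are named in advance, but the detailed progression criteria are deferred until recruitment and follow-up are complete, so the thresholds can be set with the results known

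*Protocol*

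**What the plan says.** Protocol section 10.1 gives the basis of the decision: "The decision to proceed to a definitive multicentre trial will be made on the basis of acceptable rates and time for recruitment and retention", together with participant satisfaction. The next sentence fixes when the detail is written: "Detailed progression criteria will be drawn up in collaboration with an independently chaired Study Steering Committee upon completion of recruitment and follow-up".

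The same section gives planning values. For recruitment: "assuming that 30% of invitees will be recruited and in order to estimate the recruitment rate with a precision of +/- 8" per cent, "30 participants will have to be recruited". For retention: "Assuming a dropout rate of 25% and having recruited 30 individuals", "the precision of the estimated retention rate during six months would be +/- 14" per cent. These are assumptions for sizing the study and are not offered as success criteria.

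Section 3.2 says that the main Stage 2 outcome measure "is to assess the feasibility of using the purpose-built cardiovascular risk reduction intervention developed in Stage 1". It lists the recruitment rate (those agreeing out of those invited) and the retention rate (those giving end-of-study data out of those recruited) as secondary outcomes. Section 10.2 says that recruitment, retention, completion of measures and satisfaction scores "will be reported using descriptive statistics with 95% confidence intervals". Sections 3.1, 3.2, 4.2, 7.1 and 10.2 contain no numerical threshold for proceeding.

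**The concern.** Stage 2 is a single prospective cohort with no blinding described. When the last six-month visit is done, the number invited, the number recruited, the time taken and the number retained are all known or can be counted directly. Criteria written at that moment are written by people who can know which side of any proposed line the study falls on.

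This is a stated rule and not detail left to a later document: a statistical analysis plan with earlier criteria would contradict section 10.1. At stake is the credibility of the decision to commit to a definitive multicentre trial. Whether a rate counts as acceptable is left open until the rate has been seen.

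**Working it through.** **Inputs.** From section 10.1: 30 recruits, 30% uptake, 25% dropout (75% retention), stated precisions of 8 and 14 percentage points. From section 10.2: 95% confidence level. From arithmetic: 30/0.30 = 100 invitees. The cut-offs, and the true rates other than 75% retention, are assumptions for illustration, because the protocol gives none.

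**Step 1. The plan's own figures.** Half-width = 1.96 × √(p(1−p)/n).

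- Recruitment: 1.96 × √(0.30 × 0.70/100) = 0.090, or 9.0 points against the stated 8.
- Retention: 1.96 × √(0.75 × 0.25/30) = 0.155, or 15.5 points against the stated 14.

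Neither stated precision is reproduced at the 95% level. That is a separate matter, and the present point does not depend on it.

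**Step 2. How wide the uncertainty is when the line would be drawn.** Suppose 22 of 30 are retained (73.3%). The Wilson 95% interval has centre (p + z²/2n)/(1 + z²/n) = 0.707 and half-width 0.151, giving 55.6% to 85.8%. The data would therefore not settle whether true retention lies above or below 60%, 70% or 80%. This does not make every threshold in that range equally defensible.

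**Step 3. How much the position of a cut matters at n = 30.** The chance of meeting a cut of at least r retained is P(X ≥ r) with X ~ Binomial(30, p).

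| True retention | r = 18 (60%) | r = 21 (70%) | r = 23 (76.7%) | r = 24 (80%) |
|---|---|---|---|---|
| 50% (assumed) | 0.181 | 0.021 | 0.003 | 0.001 |
| 65% (assumed) | 0.780 | 0.358 | 0.124 | 0.059 |
| 75% (planning value) | 0.978 | 0.803 | 0.514 | 0.348 |
| 90% (assumed) | 1.000 | 1.000 | 0.992 | 0.974 |

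At the planning value the chance runs from 98% to 35% across these cuts. At 50% it is low for every cut, and at 90% it is high for every cut.

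**Step 4. Recruitment.** With X ~ Binomial(100, 0.20), that is 100 invitees and an assumed true uptake of 20%, cuts of 15, 20, 25 and 30 recruits are met with probability 0.920, 0.540, 0.131 and 0.011.

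**Step 5. What these figures do and do not show.** They are probabilities for cuts fixed beforehand. They show how sensitive the decision is to the cut, and that sensitivity would remain after the fix. They do not measure the bias from choosing late. If the cut is chosen after the data are seen, no chance of a wrong decision to proceed can be calculated at all, and that is what fixing the date restores.

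**The case against.** The strongest reply is that the plan is not empty. The decision domains are named in section 10.1, the recruitment and retention rates are defined in section 3.2, and the word used is detailed criteria, which suggests refinement of a stated basis. The committee is independently chaired. The analysis is descriptive with no hypothesis test, so the evidence lies in the estimates and intervals, which do not depend on when a threshold is set. Section 14 promises a public report and an anonymised participant-level dataset, so others can judge the rates themselves.

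All of this stands, and it limits the point. A reader might infer that criteria set this way cannot be failed, that a favourable conclusion would carry no evidential weight, or that the choice of cut alone decides the answer. The documents do not support these readings. Very poor or very good retention gives the same decision under any cut in the table, the estimates keep their value, and nothing shows that thresholds will in fact be fitted to the results.

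The reply does not answer the timing. An independent chair who has seen the rates is still choosing a threshold with the rates known, and the criteria are to be written jointly with the committee, not by it alone. A named domain without a number leaves the decisive choice open. Nor is flexibility a reason to wait, since an amend band provides it.

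**Conclusion.** The point holds in this limited form: the domains are fixed in advance, the thresholds are not, and section 10.1 places them after the results exist. This permits a biased decision on proceeding; it does not show one. It leaves the Stage 2 estimates and their confidence intervals intact.

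The size is material where true rates lie near the planning values, with a chance of passing between 98% and 35% across plausible retention cuts at 75%, and small where rates are clearly poor or clearly good. This rests on independent participants, all 30 recruited, and illustrative cuts that are not the protocol's. It affects no participant's safety or treatment. It should be fixed, but it does not undermine the study.

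**What to change.** In section 10.1, replace the closing words that place the criteria after recruitment and follow-up with: *before the first Stage 2 participant is enrolled*. The protocol does not make clear whether Stage 2 is already open. If it is, set the criteria before recruitment and retention data are summarised for the committee, which is more workable than trying to hide running totals in an open single-cohort study.

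Record, with the date of approval, proceed, amend and stop bands for the domains section 10.1 already names: recruitment rate, retention rate, time, and participant satisfaction. No further domains and no rearrangement of section 3.2 are needed to cure this defect.

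The planning values of 30% uptake and 75% retention may inform the bands but should not serve as hard pass marks. A 75% cut means at least 23 of 30 (0.75 × 30 = 22.5, rounded up), and it is met only about 51% of the time when true retention is exactly 75%. A cut of 30 recruits from 100 invitees is met about 54% of the time when true uptake is 30%.

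The cost is one agenda item and a short amendment. The protocol already has its Study Steering Group meeting at least six-monthly (the section on study management committees) or three-monthly (section 9.4), so no extra meeting should be needed if that group is the committee meant in section 10.1. The team loses the freedom to choose thresholds afterwards; the amend band, and documented reasons for any departure, keep room for judgement.
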